They will meet face-to-face at least once a year and maintain and approve minutes of meetings. Every 30 participants.

3. Describe the events that would trigger an unscheduled review. Also include stopping guidelines and un-blinding rules if applicable.

Events where the participant became extremely distressed as part of the research procedure or expressed suicidality or if they were a harm/threat to self or others. The Data Safety and Monitoring Plan (attached, submitted in the NIH grant that funded this application), we provide specific guidelines to assess suicidality or harm to others. The research staff would follow all
procedures to ensure the safety of the participant. And the DSMB would be

4. List who will be *locally* monitoring and collecting information on adverse events and/or unanticipated problems (e.g., UCI Lead Researcher, Research Coordinator, etc.). Include the name, title and experience of the individual(s) and further describe each individual's role in the oversight of subject participating in the study.

The Principal Investigator ([name] [name]) will be responsible for locally monitoring and collecting information on adverse events and unanticipated problems. [name] will be onsite during participant recruitment and during the administration of intervention procedures. In the event that [name] is not able to be onsite, a senior staff will be in contact directly with [name] should any problems arise. Moreover, when [name] is not onsite, staff will report daily on study progress and any potential issues. [name] will monitor all data weekly.

5. Describe the plan for annual reporting of the participants' safety, and the study's conduct, progress, and efficacy, when appropriate. *Note: At the Continuing Review, please provide all relevant documentation related to the review of the accumulated data for safety. For the case your submission includes a DSMB charged with the oversight of data safety, include all available DSMB reports as part of your submission.*

Annual reporting will occur at the DSMB meeting. The Principal Investigator will keep detailed notes from the meeting and evaluate the study's conduct (e.g., any unanticipated problems), progress (e.g., recruitment, retention), and efficacy (e.g., results of any preliminary data analyses).

DATA SAFETY AND MONITORING PLAN

Possible Serious Adverse Events or Adverse Events

Serious adverse events

• Suicide attempt, severe violence to another person

Other adverse events

- Inadvertent disclosure of illegal immigrant status
- Adverse reaction to stress task

Risk Management Protocols in Place to Deal with Adverse Events

- Date Safety and Monitoring (DSM) issues are raised at quarterly meetings with all research staff
- Events will be reported as they occur
- A certificate of confidentiality will be secured.
- Research staff will administer the questionnaires individually.
- Participants will be cautioned not to disclose any confidential information within the group sessions.
- Unique identifiers are used on all data. Access to identifiers is restricted to the study PI, lead mentors and data manager by a combination lock.

Data and Safety Monitoring Procedures

- Serious adverse events (SAE) must be reported to the NIH Project Officer (PO) by email or telephone within 24 hours of the SAE. A more complete written report documenting the event must occur within 72 hours of the event.
- All adverse events will be reported by email to the NIH PO twice a year: six months after the Notice of Grant Award (NGA) and at the end of the budget year.

Data Safety and Monitoring Board (DSMB)

The board will be composed of six members, including the PI, mentors ([name], [name], [name]) and two mid-level to senior investigators from our institution with psychological expertise ([name] and [name]). They will meet face-to-face at least once a year and maintain and approve minutes of meetings. The NIH PO will be kept informed regarding changes to the membership of the DSM board. Data will be reviewed as every 30 participants enter the study.

Training for all staff

During the orientation prior to start of the grant, all research staff and research assistants will be trained on recognizing all types of potential crises, how to make a thorough assessment, and role play protocols that are featured below and in the DSMB section. During these meetings, in services that address mental health crises and associated symptomatology will be provided to enhance the staffs' ability to confidently engage in the protocols for participants who may be experience psychiatric or psychological distress. All research assistants will also meet weekly with the PI to review challenging interactions, circumstances, or situations that may have arisen with the participants. Discussions will focus on how the incident could have been handled differently and what the ideal outcome for that situation might have been.

Training in Red Flag Procedures

Research staff will be trained to assess and react as follows:

RED FLAG – SUICIDE

During your work as a research staff, you may encounter a respondent who expresses suicidal intentions, or you may suspect that a respondent may be suicidal. Be sure to document all the information in sections I and II as you will need to provide that information to the treatment program counselor or on-call clinician.

- I. Is this person a suicide risk?
 - _____ The individual is currently thinking about suicide.
 - The individual has a plan and the means to commit suicide.
 - _____ The individual has attempted suicide in the past.

If any of the above are true or if you suspect the client is suicidal, also note if:

- The individual is currently exhibiting serious depression/anxiety.
- The individual is experiencing stressful life events.
- II. Assessment of support system:
 - a) Is the individual under professional care (i.e., psychologist, psychiatrist, counselor)?
 - b) Does the individual have a social support network (i.e., friends, family, sponsor)?
 - c) Has the individual talked with any of the members of his or her social support network in the last 30 days?
 - d) Is the individual able to talk about this issue with his or her support system?
 - e) Is the individual aware of available social service programs?
- III. If the person appears to be suicidal or has attempted suicide since the last interview:
 - a) Let the respondent know that you are concerned, and that you need to inform a clinician and your supervisor.
 - b) If you are not at a treatment program, have the client wait with you or hold on the line while you take the following steps:
 - If the client has indicated that he/she is under professional care, ask the client for permission to contact his/her clinician and, if permission is granted, obtain the clinician's contact information. Be sure to document the client's permission and clinician contact information, you will need to provide it to the on-call clinician who will confirm client permission and make the contact.
 - 2) Contact the on-call clinician at the Los Angeles County Mobile Crisis Response Team (MCRT); ______. A clinician is on call 24 hours a day. Provide the clinician with all the suicidality information you have gathered. Facilitate phone contact between your client and the MCRT clinicians. The clinician will make the decision about what steps to take with this client. Document the details of the clinician call.
 - d) Report back to the PI immediately.
 - Your Principal Investigator [name], [contact]

The situation will be evaluated by the group and a decision will be made if it should be reported to the LAC MCRT; they will advise us on how we need to proceed.

- e) If the person attempts to harm himself or herself in your presence, contact the police (911). The police may place the person in a psychiatric facility for a 72-hour observational hold. Get the police report number.
- f) Complete an Incident Report detailing the problem and action taken. Be sure that the Incident Report is placed in the respondent's file.

g) Make arrangements to follow-up on your client's status with the treatment program counselor, supervising counselor, or on-call clinician within the next seven days.

If the MCRT is called, an assessment will be done by the MCRT staff at the location of the participant. Based on the assessment of the MCRT, the participant may be transported to a hospital for inpatient treatment. If it is determined that the person does not need to be hospitalized, the participant will be referred to the outpatient services at the neighborhood clinic. If the participant is at the same location as the staff, the staff will find out if the participant has taken any active steps such as already having taken pills, etc. If the participant is not in immediate danger, the staff will find out the following: history of drug and alcohol abuse; history of familial suicide; history of familial mental illness. The staff will find out if the participant has a plan for how he would commit suicide. If she does have a plan, the staff will find out if she/he has any weapons, pills, etc, and remove all weapons from her possession, and explore the nature of her various plans. The PI, once they have arrived, will continue to focus on the reasons the participant of those of his outside support system with whom he wishes to be in contact, for future use in case of another emergency. The research staff will collaborate with the treating psychiatrist to facilitate referral and follow through with a counseling psychiatrist/psychotherapist after discharge from the hospital. The staff/PC will document each step of this process.

If it is determined that the person does not need to be hospitalized, any additional treatment will be facilitated with Prototypes staff. To facilitate communication the participant will be asked to sign a Release of Information. If the participant provides a Release of Information, the PC will follow-up to ensure that the participant is receiving the necessary treatment. Depending on the outcome of the event, the PI may recommend that the participant withdraw from study participation. The staff/PC will document each step of this process in an adverse event log.

In addition, the DSMB will be informed of reports of suicidal ideation and current or recent abuse, reported by the staff to the proper authorities. Further, the DSMB will monitor that these reports are made expeditiously and with the full knowledge of the respondent. Monitoring information is also provided in the HSPC segment of this application.

Harm to others

I. Is this respondent dangerous to others?
The individual expressed intent to harm or kill a specified person.
The individual has the means (gun, knife, etc.) to harm that person.
The individual has a thought-out plan.

II. If you feel that the person is dangerous to others, and is likely to follow through with his/her plans:

Assess the situation. If it is safe, complete the study protocol is the participant desires. Report the information to your supervisor, the PI and the licensed clinician on staff at Prototypes. If you

feel unsafe or are not sure about it, complete the research procedures; only if possible. But if the situation is volatile, terminate immediately. Try to be as graceful and subtle as possible. For example, complete the specific task you are on or make up some reason for leaving, and say you will have to reschedule the rest of the procedures. Pay the subject in full, or leave immediately if you don't feel safe to do so. Trust your sense of the situation, and act accordingly.

Report back to your supervisor or call in immediately. If something takes place outside of the work hours, call your supervisor at home. The supervisor should then immediately contact the project's PI. Supervisors are:

Your Principal Investigator [name] [name]., [contact]

The situation will be evaluated quickly by the group and a decision will be made if the LAC MCRT needs to be called; they will advise us on how we need to proceed. If the situation is reported to the police, get the report number from the police.

III. Complete an Incident Report. Be sure to put a copy of the Incident Report in the respondent's file so that those working with the file in the future know an incident occurred. Aside from the DSMB, the PI will carefully monitor the data weekly.

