 - Homework: Body Scan recording using MP3 player; eating one meal mindfully; optional informal meditation practice. Participants will also complete a trauma-informed safety plan to ensure that, although MBSR is given in a group format, the MBSR trainer is responsive to the unique needs of the individual.
- Week 2: Understanding Perceptions. This session focuses on self-responsibility and short and long-term changes for health enhancing behaviors; how you see things determines how you react or respond.
 - **Homework**: Body Scan recording using MP3; fill out Pleasant Events Calendar; select one activity to bring full awareness to.
- Week 3: Hatha Yoga, Sitting Meditation, Walking Meditation. The theme is the pleasure and power of being present; this week teaches how to investigate the mind and body through yoga and meditation.
 - **Homework**: Alternate Body Scan recording with Lying-down Yoga using MP3 player; fill out Unpleasant Events Calendar; sitting meditation.
- Week 4: Concentration and Awareness. This theme relates to how conditioning and perception influence one's experience and new ways to relate to stress.
 - **Homework**: Alternate Body Scan recording with Lying-down Yoga using MP3 player; be aware of being stuck, sitting meditation.
- Week 5: Unhealthy Patterns and Getting Unstuck. This week examines conditioned patterns and the passive ways that people cope (e.g., numbing, denial, passive-aggressiveness, suppression of feelings, substance dependency).
 - **Homework**: Fill out Difficult Communications Calendar; Sitting Meditation and Standing Yoga Sequence.
- Week 6: Transformational Coping Strategies. This week includes how to deal with stressful communication and knowing and expressing your feelings.

- **Homework**: Alternate Sitting Meditation recording with Body Scan and/or Standing or Lying down Yoga recording.
- Week 7a: Retreat. This will be a silent class, with sitting and walking practice. Guided meditations will include loving-kindness meditation.
- Week 7b: Maintaining Discipline and Flexibility. This class focuses on how to more fully integrate mindfulness into daily life. Instructors and participants discuss lifestyle choices and limiting patterns.
 - **Homework**: no recordings; try to practice formal sitting meditation; recordings can be used if necessary.

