- Week 8: Course Review. In this session, students will reflect on the course, the instructor will provide additional resources, and participants will discuss their experiences with the group.

Subsection 2.13 - Phase II Health Promotion Intervention

The Health Promotion program is eight weeks long with one 1.5-2 hour session per week (the seventh week has two sessions to ensure the same number of contact hours as the "mini-retreat" in the MBSR course). The Health Promotion Classes were designed to be analogous to the MBSR classes in terms of length and contact hours. This is because the effect of being in a group and participating in a study could help participants, without the benefit having much – if anything – to do with the actual intervention.

The program will be run by a UCI graduate or postbac student with a BA or higher. The SMART (Specific Measurable Achievable Relevant Time-based) framework will be used for goal setting. In this framework, specific, achievable goals are outlined by the participant as relevant to each class. This helps with information retention and helps reinforce concepts and positive behaviors. Snacks and drinks will be provided.

Each week in the Health Promotion program focuses on a different theme. The sessions are as follows:

- 1. Introduction & overview
- 2. Envisioning Health through Art
- 3. Chronic Disease I Heart Health
- 4. Chronic Disease II Diabetes
- 5. Nutrition and Hydration
- 6. Infectious Disease Prevention
- 7. Skin Care
- 8. Oral Health
- 9. Promoting Social Integration & Course Graduation

Subsection 2.14 - Phase II Post-Assessment

After the ninth session (of either MBSR or Health Promotion), a post-assessment will be administered via tablet. Urine will again be collected to validate self-report drug use. Participants will repeat the brief stress task (Trauma Imagery Task) using an identical strategy and provide saliva samples before and after. The Lead Researcher or a postbac student researcher will be on site to answer any questions or clarify any items. Urine and saliva samples will both be stored in a freezer on-site or at [name] research office and then transferred to UCI for analysis within 36 hours. Follow-ups will occur on site unless participant has moved to sober living or other location. Zoom or phone will be implemented for those who moved out of state

Subsection 2.15 - Phase II Team Management of Biospecimen Collection Refusal

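### In the available text the two named SAEs are not asked about at any scheduled assessment, and both SAE reporting deadlines run from the event instead of from staff awareness

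*Combined protocol and SAP*

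**What the plan says.** All of the following is in the protocol's Appendix III unless stated otherwise.

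- **Serious events.** The list reads "Suicide attempt, severe violence to another person". The other adverse events listed are inadvertent disclosure of immigration status and an adverse reaction to the stress task.
- **Deadlines.** "Serious adverse events (SAE) must be reported to the NIH Project Officer (PO) by email or telephone within 24 hours of the SAE". For the written report: "A more complete written report documenting the event must occur within 72 hours of the event".
- **Trigger.** The suicide procedure begins when a respondent voices intent or staff suspect risk. One step applies "If the person appears to be suicidal or has attempted suicide since the last interview".
- **Review and admission.** Unscheduled board review follows "Events where the participant became extremely distressed as part of the research procedure or expressed suicidality", or a threat to self or others. In the suicide procedure, "the participant may be transported to a hospital for inpatient treatment". Reports of suicidal ideation go to the board.
- **Collection.** The principal investigator is responsible for collecting adverse events, with daily staff reports when absent. No form or question for asking participants is described.
- **Assessments.** Section 2.8 sets out 17 items in order, and Appendix IV describes the measures.
- **Active enquiry that does exist.** The debriefing script (Section 2.10 and Appendix II) asks about current distress after the stress task. Section 2.2 and Appendix IV update traumatic and negative life events at follow-up.
- **Analysis.** The SAP models the primary and secondary outcomes. It mentions no tabulation of harms.

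**The concern.** The plan names suicide attempt as an SAE and has a step for attempts made since the last interview, yet no scheduled item is described that would bring one to light. Capture then depends on what a woman volunteers or what staff notice, and it is weakest after the course ends, when women may have moved away. A deadline counted from the event cannot be met for an event that becomes known weeks later, so staff who follow the plan correctly would still be in breach.

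Two things are at stake. Serious events may go unrecorded in trauma-exposed women who repeat a trauma-imagery task at each assessment. And if harms are later compared by arm, passive capture leaves room for disclosure to differ. In the MBSR course, "Participants will also complete a trauma-informed safety plan" and the instructor is experienced with PTSD (Section 2.12). For the control classes, "The program will be run by a UCI graduate or postbac student with a BA or higher" (Section 2.13).

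**Working it through.** **1. Events against scheduled enquiry.** The documents give no adverse event rate or count to reproduce, so the first check sets passages side by side.

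| Event | Place in Appendix III | Scheduled enquiry described |
|---|---|---|
| Suicide attempt | SAE list; red-flag step | None |
| Severe violence to others | SAE list; harm-to-others procedure | None |
| Expressed suicidality | Review trigger; ideation reported to the board; in neither event list | None |
| Hospital admission | Foreseen in the red-flag procedure; in neither event list | None |
| Stress-task reaction | Other-event list; review trigger if extreme | Yes, debrief question |
| Harm from a class | Not listed | Open free-response prompt only (Appendix IV) |

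None of the 17 items in Section 2.8 and no Appendix IV measure is described as covering suicidality, hospital stay or adverse events. PROMIS Depression is described by mood, self-view, positive affect and anhedonia. The 40 life events are described only as trauma and stressors; the items are not shown.

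**2. Length of the unobserved gap (T2 to T3).** Section 2.7 gives assessments at 2 and 6 months: 6 - 2 = 4 months, and 4 x 30.4 = 121.6 days. Table 4 in Section 2.3 puts the last one 6 months after the intervention: 365 / 2 = 182.5 days.

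**3. Share of events still in time.** Assume that an event is equally likely on any day of a gap of g days and is learned of only at the next contact. The share within 24 hours is then 1/g, the share within 72 hours is 3/g, and the mean delay is g/2.

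| Gap | 24 h | 72 h | Mean delay |
|---|---|---|---|
| 121.6 days | 1/121.6 = 0.8% | 3/121.6 = 2.5% | 61 days |
| 182.5 days | 1/182.5 = 0.5% | 3/182.5 = 1.6% | 91 days |
| 7 days (weekly class) | 1/7 = 14% | 3/7 = 43% | 3.5 days |

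**4. Who is seen.** Section 2.16 reproduces as a chain: 448 x 0.30 = 134.4 (stated 134); 134 x 0.90 = 120.6 (stated 120); 134 x 0.90 x 0.80 = 96.5 (stated 96). So 134 - 96 = 38 women (28%) are not expected at T3. If losses are cumulative, as the chain implies, 120 - 96 = 24 of those 38 are still expected at T2, and 134 - 120 = 14 (10%) at neither follow-up.

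**5. Harms by arm.** If the true risk ratio is 1, the apparent ratio is the ratio of detection rates. Detection rates are assumed here for illustration: 70% v 70% gives 1.0; 80% v 70% gives 1.14; 90% v 60% gives 1.5. The documents fix neither the rates nor which arm would be higher.

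**The case against.** Several stronger readings are tempting, and the documents do not support them.

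- **That harms are recorded only when volunteered or noticed.** The debrief asks directly about distress in both arms, and the task is repeated at every assessment (Section 2.1). Life events are updated at both follow-ups, and a free-response prompt invites comment. This stands, and it covers the listed stress-task reaction. But the debrief asks about the present moment, and the life-event update is collected as adversity history with no stated link to adverse event reporting.
- **That the plan cannot show whether MBSR worsens symptoms.** It can. The PCL-5 and PROMIS Depression are modelled by group, time and their interaction in the SAP.
- **That harm counts by arm are unreliable.** The SAP plans no such counts. Contact is matched across arms, staff share crisis training, and women in both arms are cautioned against confidential disclosure in class. Differential disclosure is possible, not shown.
- **That the event lists flatly contradict the rest of Appendix III.** The list is headed as possible events and is not said to be exhaustive. Ideation reports already reach the board, and incident reports and an adverse event log exist. What remains is that the lists, review triggers and logs do not name the same events.
- **That the 38 women are never seen.** Most are expected at T2.

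Two further points limit the claim. Women live at staffed sites when recruited, so word may reach the study sooner, although no route from site staff to the study team for SAEs is described. And part of Appendix III, the 40 items and the REDCap forms of Appendix VII are not in the text available, so a relevant question there cannot be excluded. Neither point alters the deadline wording.

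**Conclusion.** The point holds in a limited form and should be acted on. Both SAE clocks run from the event, while the same appendix foresees learning of an attempt at a later interview; this is plain in the current text. It is also plain that no scheduled question on the two named SAEs is described, subject to the unseen forms. Confidence is medium for that reason.

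The size for the T2-T3 gap is 0.5-0.8% of events known within 24 hours and 1.6-2.5% within 72 hours. This rests on uniform timing and discovery only at T3. It is the unfavourable end: weekly contact during the course gives 14% and 43% under the same assumptions, and notice from any other source would raise all these shares.

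A reader might infer that off-site attempts will be missed or reported late as a rule. The documents support only that they can be. Likewise, a comparison of harms by arm would be exposed to differing disclosure, but neither its direction nor its size can be derived.

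**What to change.** 1. Check the REDCap forms first. Unless they already contain them, add a short fixed set of questions, identical in both arms, at T1, T2 and T3: suicide attempt, suicidal thoughts, hospital or psychiatric stay, serious violence, and distress from a class since the last interview, each with a date.
2. Run the 24- and 72-hour reporting clocks from the time study staff become aware, and record the event date as well, so that reporting delay and time of onset can both be read from the data.
3. Reconcile the serious and other event lists in Appendix III with its unscheduled-review triggers and its provisions on hospital admission and suicidal ideation, so that one set of events is logged and reported.
4. Tabulate these events by arm for the board and the final report, and say so in the SAP.

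The cost is an estimated 1-2 minutes per visit, a few form items and a wording edit in Appendix III and the SAP. The downside is more positive answers for staff to handle under the existing red-flag procedure. The changes concern data capture and reporting, not clinical care.

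### The PI and mentors sit on the DSMB and the PI may evaluate preliminary efficacy at its annual meeting while recruiting into known arms; the visible text describes no closed session or firewall

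*Combined protocol and SAP*

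**What the plan says.** **Board.** Appendix III, under the DSMB heading: "The board will be composed of six members, including the PI, mentors" (three removed names follow), and "two mid-level to senior investigators from our institution with psychological expertise". The mentors are close to the data: "Access to identifiers is restricted to the study PI, lead mentors and data manager".

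**Meetings.** "They will meet face-to-face at least once a year and maintain and approve minutes of meetings". Separately, "Data will be reviewed as every 30 participants enter the study". Section 2.21 also has the board meeting after every 30 enrolments, but the sentence stating the purpose breaks off.

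**Efficacy.** Item 5 of the Appendix III form states: "Annual reporting will occur at the DSMB meeting". There the PI keeps the notes and evaluates the study's conduct, its progress and "efficacy (e.g., results of any preliminary data analyses".

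**The PI's role in the trial.** Item 4 makes the PI locally responsible for collecting adverse events and says that the PI "will be onsite during participant recruitment and during the administration of intervention procedures". It also has the PI monitoring all data weekly.

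**Knowledge of arm.** Section 2.2, item 2, randomizes the sites before recruitment and gives each woman one of two consent forms according to her group. Section 2.1 makes this a site allocation within each cohort. It also claims blind evaluators, but no blinding procedure is described.

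**Interim rules.** Item 3 of the form asks for stopping guidelines and unblinding rules. The visible answer gives neither and breaks off mid-sentence. The SAP mentions no interim analysis.

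**The concern.** A monitoring board is meant to see accumulating data so that those running the trial need not. Here the PI belongs to the board, evaluates preliminary efficacy at its meeting, and is present when women are recruited and classes are delivered. The PI knows which arm each site is receiving.

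An early impression of which arm is doing better could then affect who is approached at each site, how flexibly classes are run, and how questionnaire items are clarified. Section 2.14 has the lead researcher or a student researcher on hand for such clarification at the post-assessment. This bias needs no formal test and no stopping decision; seeing the results is enough.

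A second risk arises only if a preliminary analysis were a significance test that could lead to a claim or a change of course. The overall type I error would then exceed the nominal level.

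On safety, the PI collects the adverse events, supervises the procedures that may cause some of them, and sits on the board that reviews them.

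**Working it through.** **1. Board composition.** The stated size is six. PI 1 + mentors 3 (removed names counted) + institutional investigators 2 = 6, which reproduces it. PI and mentors: 4/6 = 67%. The count of three mentors rests on the removed names. The presence of the PI and mentors does not.

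**2. Whether a meeting falls inside recruitment.** As far as the timeline table in Section 1A can be read, cohort 2 is recruited in January 2021 and cohorts 6-7 in June 2022, a span of 18 months, with cohort 1 earlier still. With at least one meeting a year, at least one should fall inside recruitment. The same table puts follow-up of cohorts 1 to 4 between April 2021 and April 2022, before cohorts 6-7 are recruited. Outcome data from both arms would therefore exist while recruitment continued.

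**3. Number of every-30 reviews.** Section 2.16: 448 × 0.30 = 134.4, stated as about 134 enrolled. floor(134/30) = 4 reviews, at 30, 60, 90 and 120. With the 130 given in Section 2.1 it is also 4.

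**4. Type I error, for illustration only.** The documents state no alpha, no boundary and no interim test. Assumptions: two-sided 0.05 at every look, independent increments, z_k = S_k/√t_k, and error = P(any |z_k| > 1.96). The placing of the annual looks is also assumed.

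| Efficacy tests assumed | Looks at n = | Overall error |
|---|---|---|
| Final only | 134 | 5% |
| One annual look + final | 67, 134 | about 8.3% |
| Two annual looks + final | 45, 90, 134 | about 10.7% |
| All four every-30 reviews + final | 30, 60, 90, 120, 134 | 13.6% to 13.7% |

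The last row requires every 30-participant review to be an unadjusted efficacy test, which the documents do not say.

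**5. Two review routes compared.** Item 5 ties efficacy to annual reporting, conditionally (any preliminary analyses). The every-30 clause speaks only of data. In Section 2.21 it follows directly on checking that data are entered accurately. Efficacy is therefore established only for the annual route.

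**The case against.** **Four interim tests.** A reader might infer efficacy looks at 30, 60, 90 and 120 women and quote an error near 13.7%. The documents do not support that. Efficacy appears only under annual reporting, where the form asks for it when appropriate. Nothing says that an analysis would be by arm, would be a hypothesis test, or could stop the trial. This objection stands, and the figure is kept only as the end of an illustrative range.

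**The PI as sole judge of safety.** This too would go too far. Serious adverse events go to the NIH Project Officer within 24 hours, with a fuller report within 72 hours, and all adverse events go there twice a year. For suicidality away from a treatment program, a crisis-team clinician decides the next steps. Harm-to-others concerns also go to a licensed site clinician. Two board members are not described as trial staff. What remains is that the board's own review is not separated from the PI.

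**An open-label trial.** The documents never use the term and they claim blind evaluators. What they do support is narrower: the consent form is arm-specific and the PI is present at class delivery, so the PI and participants know the arm.

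**Missing text.** Part of Appendix III was not available and the item 3 answer is cut off. A closed session, firewall or stopping rule can be called absent only from the visible text. The board composition and the efficacy clause are positive statements and do not depend on what is missing.

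**Keeping all by-arm data back.** A complete bar on by-arm outcomes could hide symptom worsening in one arm from the board. That is fair, and the fix allows for it.

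**Conclusion.** The concern holds as a matter of monitoring structure. The PI and mentors sit on the board, apparently in four of six seats. The PI may evaluate preliminary efficacy at the annual meeting while present at recruitment into arms known before consent. The visible text describes no arrangement that keeps by-arm results from the people running the trial.

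The main consequence is a possible bias in conduct, which the documents give no means of sizing. Inflation of type I error is conditional: none if no efficacy test is made, and about 8.3% to 10.7% if one or two unadjusted annual tests could lead to a claim. Those figures rest on an assumed alpha of 0.05 and on independent increments. They do not represent allocation by site within cohort, so they describe the effect of repeated looks alone and do not certify 5% for the SAP's final model.

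**What to change.** In Appendix III:

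- **Item 5.** Delete preliminary efficacy from the annual report that the PI evaluates. State that outcome data by arm are not shown to the PI, mentors or recruiting staff before the last 6-month assessment.
- **DSMB section.** Send by-arm safety data, including any symptom worsening, in closed session only to board members without a trial role (the two institutional investigators, if they have none). The PI and mentors attend open sessions and do not vote.

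**Cost.** This is an amendment to the monitoring plan, with no change to sample size, measures or procedures. The efficacy deletion needs no new members. Removing votes from the PI and mentors leaves two voters from the same institution unless up to four seats are refilled by colleagues outside the trial.

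**If the trial is complete.** The SAP is written in the past tense, so an amendment may come too late. In that case the report should state whether any interim analysis by arm was done, when, and who saw it.
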